3.1.2 Years 2 Through 4 (Active-Treatment Dose-Blinded Portion of the Study)

Prior to Infusion 14 (the first dose of Year 2) at Week 52, subjects who received placebo in Year 1 will be randomized into 1 of the active-dosing arms for Year 2; these subjects will receive BIIB054 in Year 2. Subjects who received BIIB054 (1250 mg or 3500 mg) in Year 1 of the study will continue with the same dose regimen in Year 2. Subjects receiving the 250-mg dose in Year 1 continued on their original dose assignment.

Subjects will receive 12 additional doses of BIIB054 (250, 1250, or 3500 mg) in Year 2 and up to 16 additional doses in Years 3 and 4. Up until the last subject in the study has had his or her last dose in Year 2 of the study (Week 96 Visit), eligible subjects will be able to continue treatment once every 4 weeks.

Subjects who complete dosing through Week 96 and the Final Visit 12 weeks after the last visit will be considered Year 2 completers in the eCRF.

CONFIDENTIAL

[figure not shown]
The information contained herein may not be used, disclosed, or published without the written consent of Biogen MA Inc.

See Figure 2 for a depiction of the duration of dosing in Years 3 and 4 for subjects continuing dosing past Week 96.

Figure 4 on protocol presents a flowchart for dosing and procedures from Week 96 through end of study, including how to determine which subjects are eligible to continue dosing past Week 96.

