4 SAMPLE SIZE JUSTIFICATION

The sample size calculation is based on changes in MDS-UPDRS Part I + II + III total score at Week 52 and at Week 72 of treatment. Based on data from the Parkinson's Progression Markers Initiative study, the placebo subject's mean and standard deviation (SD) at Week 52 and Week 72 are assumed to be 8.0 (10.64) and 9.6 (13.7) respectively. Assuming a maximum of 55% reduction in the change from baseline in the active group with maximum response relative to placebo group, the mean (SD) for this active group will be 3.2 (10.64) and 3.84 (13.7) respectively at Week 52 and Week 72, and the responses for other active groups are assumed to be somewhere between 0 and the maximum response. The primary analysis will be based on the MCP-MOD method to detect a dose-response trend while controlling for multiplicity. Optimal contrasts will be constructed to detect potential dose-response trend under common dose-response curves (e.g., E_{max} , exponential, logistic, linear in log dose, and quadratic model, which are illustrated with parameters shown in [Figure 4.1](#) which will be used for both Week 52 and Week 72). The planned enrollment is 311 subjects total (24 subjects in Cohort A and 287 subjects in Cohort B, [4.1](#)). Actual enrollment is 357 subjects. In Cohort A, 29 subjects were randomized in a 1:1:1:1 ratio to each of the treatment groups, while in Cohort B 328 subjects were randomized in 2:1:2:2 ratio to the placebo, 250 mg, 1250 mg, and 3500 mg groups. Based on the actual enrollment, the estimated number of subjects by cohort and treatment groups are given in [Table 4.4.2](#) below. After accounting for dropout rate of 10% and 15% at Week 52 and Week 72, respectively, the estimated sample sizes are given in [Table](#) and [Table 1](#). With the updated sample size, the study will provide an average power of approximately 80% to detect the dose-response trend over 1 year of treatment, based on a 2-sided type I error of 0.05 and approximately 73% of power at the Week 72 analyses, based on a 2-sided type I error of 0.05. Overall, the sample size in the study will provide approximately 89% power, taking into consideration success at either Week 52 or Week 72. The final candidate models for the MCP-MOD are prespecified and described below.

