A multiple comparison adjustment method will be applied to control the overall type I error at 0.05 in the study, due to the primary endpoint of change from baseline in MDS-UPDRS total score being analyzed at Week 52 and Week 72, and superiority against placebo is considered reached in the study if statistically significant result is achieved at either timepoint at the respective adjusted alpha-level.

An improved fall-back procedure will be used to control the overall type I error at 0.05 level due to multiple-testing. An alpha of 0.04 will be allocated to the Week 52 primary endpoint analyses and an alpha of 0.01 will be allocated to the Week 72 primary endpoint analysis.

- If the Week 52 analysis is statistically significant at the 0.04 level (i.e. p-value ≤ 0.04), the alpha of 0.04 will be transferred (recycled) to the Week 72 analysis, and Week 72 will have alpha=0.05.
- If the Week 52 analysis is not statistically significant at the 0.04 level, alpha of 0.01 will be used for the Week 72 analysis. Statistical significance is considered achieved if the p-value is ≤ 0.01 at Week 72.
- If statistical significance is achieved at the Week 72, in either scenarios above, then the alpha of 0.01 will be transferred (recycled) back to Week 52, and the Week 52 primary analysis will be re-evaluated for statistical significance at the 0.05 level. This will only change the conclusion of the Week 52 results if the initial p-value is greater than 0.04 and ≤ 0.05 .

No additional multiplicity adjustments will be made for secondary or [REDACTED] endpoint analyses.

A blinded sample size re-estimation may be conducted when approximately 10% of subjects have completed the Week 52 Visit or approximately 1 month before enrollment is projected to be completed, whichever is earlier (description of method is below). The study sample size may be increased based on this blinded data review. There may be small adjustments to the percentage depending on actual enrollment rate. As of the finalization of protocol Version 8 (Aug 2020), all subjects have completed Week 52 visits, this analysis was not conducted.

Blind sample size re-estimation

The sample size for this study may be reassessed in a blinded manner in a cutoff date of February 2020, by which time approximately 78/311 (25%) of subjects will complete the Week 52 visit.

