4.3.2 Primary efficacy endpoint analysis

The estimand of the primary analysis for MDS-UPDRS Part I+II+III total score at Week 72 is the mean difference of the change from baseline at Week 72 between treatment groups in the ITT population regardless of whether start of PD medication had occurred or not. Specifically, the estimand takes the following into consideration:

- A. Population: ITT population as defined in Section 4.1.1;
- B. Variable: change from baseline to Week 72 in the MDS-UPDRS Part I+II+III total score;
- C. Intercurrent events: regardless of whether start of PD medication had occurred or not;
- D. Population-level summary: difference in variable means between each early start group and delayed start group

Change from baseline in the MDS-UPDRS Part I+II+III total score at Week 72 will be analyzed using an MMRM model for all the visits in the placebo-controlled and DBE period.

Data after subjects start PD medication will be included in the primary analyses.

For details on the model to be used please refer back to the Year 1 SAP, for the analyses of MDS-UPDRS including data after PD medication. Adjusted means for each treatment group,

CONFIDENTIAL

The information contained herein may not be used, disclosed, or published without the written consent of Biogen MA Inc.

	Statistical Analysis Plan Dose Blinded Extension Period	V2.0
---	--	-------------

pairwise adjusted differences for the comparisons, 95% confidence intervals for the differences will be presented at each visit, and p-values will be presented for the key visits of week 24, 52, and 72. Dose-response testing will be done using the adjusted mean with the pre-specified MCP-MOD procedure with pre-specified candidate models (refer to Year 1 SAP Sample Size Consideration section). If the distribution of the outcome is highly skewed, p-value will be generated from the MMRM model based on the rank data. Missing data are assumed to be missing at random behind the MMRM model.

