A multiple comparison adjustment method (graphical procedure) will be applied to control the overall type I error at 0.05 in the study, due to the primary endpoint of MDS-UPDRS total score being analyzed at Week 52 and Week 72, and superiority against placebo is considered reached in study if statistically significant result is achieved at either timepoint. Please refer to the “Interim Analysis” section for this method. Pairwise comparison of each active group versus delayed-start group(s) will also be conducted, however, no additional multiplicity adjustment will be made, and nominal p-values will be reported. The primary comparison is between each of the early-start BIIB054 dose group, with the pooled delayed-start BIIB054 group.

The following three comparisons will be evaluated for the long-term efficacy analyses of BIIB054:

- The early start 250 mg compared with the pooled delayed start group;
- The early start 1250 mg compared with the pooled delayed start group;
- The early start 3500 mg compared with the pooled delayed start group

The following comparisons may also be evaluated:

- The early start 250 mg compared with the delayed start 250 mg;
- The early start 1250 mg compared with the delayed start 1250 mg.
- The early start 3500 mg compared with the delayed start 3500 mg.

Per design, a subset of subjects will enter year 3 and 4 for a limited time. There will be some visits with too few data in year 3 and 4. If this is the case, the visits with too few data will be excluded from the MMRM analyses, Otherwise, the MMRM model will not converge. In addition, since most patients will start PD medication by year 1, most data in year 2-4 will be after PD medication. Therefore, data after subject start PD medication will be included in the MMRM analyses. Otherwise, the MMRM model will not converge.

Data at the common visits of cohort A and cohort B will be included in the by visit summary and MMRM model. Data at all visits will be listed.

CONFIDENTIAL

The information contained herein may not be used, disclosed, or published without the written consent of Biogen MA Inc.

	Statistical Analysis Plan Dose Blinded Extension Period	V2.0
---	---	-------------

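### A Week 72 win is labelled superiority over placebo and powered at 73% against an untreated arm, although the comparator at Week 72 is a delayed-start group already receiving BIIB054

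*SAP*

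**What the plan says.** **Switch at Week 52.** Year 1 SAP, Section 3.1.2: before the first Year 2 infusion, "subjects who received placebo in Year 1 will be randomized into 1 of the active-dosing arms for Year 2". The extension SAP repeats this in Section 2.1.2.

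**Estimand at Week 72.** Extension SAP, Section 4.3.2: the population-level summary is the "difference in variable means between each early start group and delayed start group", regardless of PD medication. The same section makes the pooled delayed-start group the primary comparator. Section 4.3.1 defines that group as everyone randomised to placebo in Year 1, whether or not they entered the extension.

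**Success rule.** Year 1 SAP, Section 6 (also Section 5.3.2.1): "superiority against placebo is considered reached in the study if statistically significant result is achieved at either timepoint", each at its adjusted alpha. Extension SAP, Section 4.3.2, has the same rule: "superiority against placebo is considered reached in study if statistically significant result is achieved at either timepoint". Section 4.10 of the extension SAP repeats it.

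**Alpha.** Week 52 is given 0.04 and Week 72 is given 0.01. Week 72 rises to 0.05 only after Week 52 has succeeded.

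**Power inputs.** Year 1 SAP, Section 4: "the placebo subject's mean and standard deviation (SD) at Week 52 and Week 72 are assumed to be 8.0 (10.64) and 9.6 (13.7) respectively". For the best active arm: "Assuming a maximum of 55% reduction in the change from baseline in the active group with maximum response relative to placebo group". The stated results are about 80% at Week 52 and about 73% at Week 72, both at two-sided 0.05, and about 89% for success at either. Extension SAP, Section 3, carries the same inputs and results unchanged.

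**The concern.** Three parts of the plan describe three different Week 72 comparators. The estimand has a delayed-start group with up to 20 weeks of BIIB054. The success rule names placebo. The power calculation uses an observational-cohort mean for untreated patients.

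The label matters most if Week 52 fails and Week 72 alone is significant at 0.01. The rule would then declare superiority over placebo from a contrast that has no concurrent placebo arm. What such a result would show is a benefit of starting a year earlier.

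The power matters because, if the drug works as the plan assumes, it also slows progression in the switched subjects. The Week 72 contrast is then smaller than the one that was powered. The 89% for either timepoint rests on the same Week 72 means.

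**Working it through.** **Inputs**
- Placebo change 8.0 (SD 10.64) at Week 52 and 9.6 (SD 13.7) at Week 72; maximum reduction 55% (Year 1 SAP, Section 4).
- Evaluable subjects (placebo / 250 / 1250 / 3500 mg): 91/48/90/90 at Week 52 and 86/46/86/86 at Week 72 (tables in Section 4).
- The seven candidate dose-response models of Appendix III.

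**Method.** For each model *m* with shape *f* scaled to a maximum of 1, the optimal contrast weights are proportional to n_i × (f_i − weighted mean of f). The statistic is T_m = Σ c_i ȳ_i / (SD × √Σ(c_i²/n_i)). The test rejects when the largest |T_m| exceeds a simulated critical value, about 2.24 at two-sided 0.05 and 2.83 at 0.01. Power is averaged over the seven models taken in turn as the truth.

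**Step 1: reproduce the plan.**
- Week 52: 0.55 × 8.0 = 4.40, SD 10.64. Power about 82%; the plan states about 80%.
- Week 72: 0.55 × 9.6 = 5.28, SD 13.7. Power about 74%; the plan states about 73%.
- The same Week 72 inputs at alpha 0.01: about 52%.

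Both stated figures come back within 2 points, using an untreated comparator at Week 72.

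**Step 2: let the switched subjects respond.** Untreated progression from Week 52 to 72 is 9.6 − 8.0 = 1.6 points. Suppose it is slowed in proportion to the effect of the subject's new dose. Then

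comparator mean = 8.0 + 1.6 × (1 − 0.55 × f̄),

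where f̄ is the average of *f* over the re-randomised doses. Only the dose-0 mean moves. The early-start means stay at 9.6 × (1 − 0.55 × f).
- All switched subjects at maximum effect (f̄ = 1): 8.0 + 0.45 × 1.6 = 8.72. Best early-start arm: 0.45 × 9.6 = 4.32. Largest gap: 4.40 instead of 5.28.
- Linear model, 1:1:1: f̄ = (250 + 1250 + 3500)/(3 × 3500) = 0.476, so the mean is 8.0 + 1.6 × (1 − 0.262) = 9.18.

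The SAP text gives no re-randomisation ratio, so three cases were run.

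| Switched subjects | Power at 0.05 | Power at 0.01 |
|---|---|---|
| Untreated (as in the plan) | 74% | 52% |
| Slowed, 1:1:1 | 67-68% | 44% |
| Slowed, 1:2:2 | 67% | 43% |
| Slowed, all at maximum effect | 62% | 38-39% |

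**Step 3: faster catch-up.** If switched subjects (1:2:2) gain 25%, 50% or 100% of the full effect of their new dose by Week 72, power at 0.05 is about 63%, 52% and 33%. At 0.01 it is about 39%, 29% and 16%.

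**Step 4: which alpha counts.** Week 72 has 0.05 only when Week 52 has already succeeded, so the study is then positive anyway. For a Week 72 result to add a success, the level is 0.01.

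**Step 5: the printed active means.** Section 4 also says "the mean (SD) for this active group will be 3.2 (10.64) and 3.84 (13.7) respectively at Week 52 and Week 72". That is a 60% reduction: (8.0 − 3.2)/8.0 = 0.60. With these means Week 52 power is about 88% and Week 72 power with an untreated comparator is about 81%, so they do not reproduce the stated pair. With a delayed-start comparator under Step 2, they give about 70-75% at 0.05 and 46-53% at 0.01.

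**The case against.** **The estimand is already disclosed.** The extension SAP defines the Week 72 contrast as early versus delayed start and names the pooled delayed-start group as comparator. This stands. The fault is narrower: the success sentence and the power inputs were not brought into line with that estimand.

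**The 73% is correct arithmetic.** It is reproduced from its inputs, and enrolment was complete at 357, so restating it changes no design decision. This also stands. The figure is optimistic for the contrast that will be tested; it is not a slip in calculation.

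**The 73% might already allow for dilution.** The printed active means with a delayed-start comparator give 70-75%. But those means give about 88% at Week 52 against the stated 80%. The 55% effect with an untreated comparator matches both stated figures.

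**Stronger readings a reader might infer, which the documents do not support:**
- *Type I error is inflated.* It is not. If BIIB054 is inert, the delayed-start group behaves like placebo and the Week 72 test keeps its level. If the drug works in switched subjects, the dilution is conservative.
- *Alpha cannot be recycled between two estimands* (without PD medication at Week 52, regardless of it at Week 72). Splitting and recycling alpha controls error across different hypotheses and needs no common estimand.
- *The whole dose-response curve shrinks to a maximum of 4.40.* Switching the placebo arm moves only the dose-0 mean. The differences among early-start doses remain, and the contrasts use them. Rescaling every arm overstates the loss.

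**Conclusion.** The mismatch is real and affects a primary decision rule. A Week 72 success is evidence for early over delayed start. It does not show superiority over a concurrent placebo group, nor the size of such an effect.

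Under the plan's 55% effect and proportional slowing, Week 72 power is about 62-68% at 0.05 instead of 73%. At 0.01 it is about 38-44% instead of about 52%. With 25-100% catch-up it runs from about 63% down to 33% at 0.05.

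These ranges rest on two assumptions that the SAP text does not settle: the effect of BIIB054 in switched subjects over Weeks 52-72, and the re-randomisation ratio. No single replacement figure is justified. The influence of PD medication on the Week 72 difference was not quantified. The 89% was not recomputed, because the correlation between the two timepoints is not given.

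**What to change.** 1. In both SAPs (Year 1 Sections 5.3.2.1 and 6; extension Sections 4.3.2 and 4.10), reserve the claim of superiority over placebo for Week 52. Define a Week 72 success as early start better than delayed start, the latter being subjects randomised to placebo in Year 1, regardless of PD medication.
2. In Year 1 Section 4 and extension Section 3, restate the Week 72 power and the 89% with a delayed-start comparator mean. Use the alpha actually available: 0.04 at Week 52, and 0.01 at Week 72 or 0.05 if Week 52 succeeds. Show the result as a range and state the assumption for Weeks 52-72. Reconcile the 55% with the printed means of 3.2 and 3.84 at the same time, since the range depends on which is meant.

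The cost is text edits and one recalculation, with no new data and no change to the testing procedure. The stated Week 72 power and the claim attached to it become less favourable.

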8.1 Appendix I: Questionnaires

Please refer to the separate Appendix document for the details of the questionnaire as well as the corresponding scoring algorithm.

8.2 Appendix II: Visit Window Mapping

Please refer to the separate Appendix document for the details of the visit window mapping rule for all the study endpoints.

8.3 Appendix III: Description of MCP-MOD method

MCP-MOD method works in the following steps.

Step 1: Set of candidate models

Candidate models include Emax (ED50=450.5), Exponential ($\delta=2850.5$), logistic (ED50=1547.5, $\delta=510.5$), linear-log (off=237.5), quadratic ($\delta=-0.0002$), Exponential ($\delta=860.5$) and Linear. The response shapes are displayed in [Figure 4.1](#) in the SAP.

Step 2: Optimal model contrast

The LSmeans at Week 52 and the covariance matrix of the LSmeans will be estimated from the MMRM model and used to determine the optimal contrasts. The coefficients of the contrasts are pre-specified during the design stage once the candidate models are selected in Step 1.

Step 3: Testing for dose response signal

A multiple contrast test will be used to test the overall dose response signal and to identify all contrasts that have adjusted p-values less than or equal to the pre-specified alpha controlling for multiplicity at Week 52 and Week 72. As a result, the significance of the dose response signal will be established.

Step 4: Model selection

Value of AIC will be presented together with the p-values for the dose response models in Step 3.

CONFIDENTIAL

The information contained herein may not be used, disclosed, or published without the written consent of Biogen MA Inc.

8.4 Appendix IV: Definition of the Early Parkinson’s Regional Progression Score (EP-RPS)

EP-RPS is derived in the following steps based on MDS-UPDRS Part III motor assessments.

Step 1: group the 30 MDS-UPDRS Part III items into 7 body regions as below (item 3.11 of freezing of gait, item of 3.13 of posture and item 3.18 of constancy of rest are excluded.)

Body region	Question items in UPDRS Part III questionnaire	Variable names in SAS data set
Right hand	3.3b Rigidity-RUE 3.4a Finger Tapping-Right hand 3.5a Hand movements-Right hand 3.6a Pronation-supination movements-Right hand 3.15a Postural tremor-Right hand 3.16a Kinetic tremor-Right hand 3.17a Rest tremor amplitude-RUE	3.3b NP3RIGRU 3.4a NP3FTAPR 3.5a NP3HMOVR 3.6a NP3PRSPR 3.15a NP3PTRMR 3.16a NP3KTRMR 3.17a NP3RTARU
Left hand	3.3c Rigidity-LUE 3.4b Finger Tapping-Left hand 3.5b Hand movements-Left hand 3.6b Pronation-supination movements-Left hand 3.15b Postural tremor-Left hand 3.16b Kinetic tremor-Left hand 3.17b Rest tremor amplitude-LUE	3.3c NP3RIGLU 3.4b NP3FTAPL 3.5b NP3HMOVL 3.6b NP3PRSPL 3.15b NP3PTRML 3.16b NP3KTRML 3.17b NP3RTALU
Right leg	3.3d Rigidity-RLE 3.7a Toe tapping-Right foot 3.8a Leg agility-Right leg 3.17c Rest tremor amplitude-RLE	3.3d PN3RIGRL 3.7a NP3TTAPR 3.8a NP3LGAGR 3.17c NP3RTARL
Left leg	3.3e Rigidity-LLE 3.7b Toe tapping-Left foot 3.8b Leg agility-Left leg 3.17d Rest tremor amplitude-LLE	3.3e NP3RIGLL 3.7b NP3TTAPL 3.8b NP3LGAGL 3.17d NP3RTALL
Trunk	3.3a Rigidity-Neck 3.9 Arising from chair 3.10 Gait 3.12 Postural Stability 3.13 Posture	3.3a NP3RIGN 3.9 NP3RISNG 3.10 NP3GAIT 3.12 NP3PSTBL 3.13 NP3POSTR
Speech	3.1 Speech	3.1 NP3SPCH
Face	3.2 Facial expression 3.17e Rest tremor amplitude-Lip/jaw	3.2 NP3FACXP 3.17e NP3RTALJ

CONFIDENTIAL

The information contained herein may not be used, disclosed, or published without the written consent of Biogen MA Inc.

[figure not shown]
Step 2: For each body region, derive the region score as the maximum score of all the items included in the region. As a result, a score will be derived per subject per visit per body region.

Step 3: For each subject at each visit, count the total number of progressed body region. A body region is progressed at visit t if and only if the change from baseline in the body region score is greater than or equal to 1 at visit t, and the change is confirmed by the next visit after visit t. A body region is progressed by visit s, if and only if the body region is progressed prior to or at visit s.

Step 4: For each subject at each visit, derive the body region progression AUC as the weighted average of the number of progressed body regions of all the visits before the current visit. The weight of each visit is proportional to the time elapsed from the previous visit to the current visit. Alternatively, the body region progression AUC at visit t can be computed as the area from baseline to visit t under the trajectory curve of the number of progressed body regions by time, divided by the total number of years elapsed from baseline to visit t. Missing data will be imputed by linear interpolation for the intermediate missing visits and by linear extrapolation for the trailing missing visits.

For illustration purpose, suppose a subject had 0, 1, 2, 2, 3, 3 and 4 body regions with progression at Week 8, 16, 24, 32, 40, 48 and 54 visits respectively, then the subject's progression AUC value is as shown in the following plot.

Number of progressed body regions over time for a hypothetical patient

CONFIDENTIAL

The information contained herein may not be used, disclosed, or published without the written consent of Biogen MA Inc.

[Redacted]

[Redacted]

[Redacted]

[Redacted]

[Redacted]

[Redacted]	[Redacted]	[Redacted]	[Redacted]	[Redacted]
[Redacted]	[Redacted]	[Redacted]	[Redacted]	[Redacted]
[Redacted]	[Redacted]	[Redacted]	[Redacted]	[Redacted]
[Redacted]	[Redacted]	[Redacted]	[Redacted]	[Redacted]
[Redacted]	[Redacted]	[Redacted]	[Redacted]	[Redacted]

CONFIDENTIAL

The information contained herein may not be used, disclosed, or published without the written consent of Biogen MA Inc.

[REDACTED]	[REDACTED]	[REDACTED]	[REDACTED]	[REDACTED]
[REDACTED]	[REDACTED]	[REDACTED]	[REDACTED]	[REDACTED]
[REDACTED]	[REDACTED]	[REDACTED]	[REDACTED]	[REDACTED]
[REDACTED]	[REDACTED]	[REDACTED]	[REDACTED]	[REDACTED]
[REDACTED]	[REDACTED]	[REDACTED]	[REDACTED]	[REDACTED]
[REDACTED]	[REDACTED]	[REDACTED]	[REDACTED]	[REDACTED]
[REDACTED]	[REDACTED]	[REDACTED]	[REDACTED]	[REDACTED]
[REDACTED]	[REDACTED]	[REDACTED]	[REDACTED]	[REDACTED]
[REDACTED]	[REDACTED]	[REDACTED]	[REDACTED]	[REDACTED]
[REDACTED]	[REDACTED]	[REDACTED]	[REDACTED]	[REDACTED]
[REDACTED]	[REDACTED]	[REDACTED]	[REDACTED]	[REDACTED]

[REDACTED]

[REDACTED]

[REDACTED]	[REDACTED]	[REDACTED]	[REDACTED]	[REDACTED]
[REDACTED]	[REDACTED]	[REDACTED]	[REDACTED]	[REDACTED]
[REDACTED]	[REDACTED]	[REDACTED]	[REDACTED]	[REDACTED]
[REDACTED]	[REDACTED]	[REDACTED]	[REDACTED]	[REDACTED]

CONFIDENTIAL

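### Appendix IV both excludes and scores posture (item 3.13) in EP-RPS, and its unbounded extrapolation can give more than the 7 possible progressed regions

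*SAP*

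**What the plan says.** The definition is in the placebo-controlled SAP, Appendix IV (section 8.4).

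- **Step 1** is to "group the 30 MDS-UPDRS Part III items into 7 body regions as below", with a parenthesis stating that "item 3.11 of freezing of gait, item of 3.13 of posture and item 3.18 of constancy of rest are excluded". The Trunk row of the table directly below reads, in part, "3.12 Postural Stability 3.13 Posture" and gives posture a SAS variable name, NP3POSTR.
- **Step 2** is to "derive the region score as the maximum score of all the items included in the region".
- **Step 3** sets two conditions for a progressed region. The first is a threshold: "the change from baseline in the body region score is greater than or equal to 1 at visit t". The second is a confirmation requirement, namely that "the change is confirmed by the next visit after visit t". The count is cumulative: "A body region is progressed by visit s, if and only if the body region is progressed prior to or at visit s".
- **Step 4** turns the counts into a time-averaged AUC and imputes "by linear extrapolation for the trailing missing visits". It states no bound and no method for fitting the line.

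Section 5.3.2.4 analyses EP-RPS by ANCOVA at Week 52, with p-values, once including and once excluding data after PD medication. Sections 5.3.3 and 5.5.7 also use EP-RPS in correlation analyses.

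**The concern.** Two programmers working from the same page would build different endpoints. One follows the parenthesis and leaves posture out; the other follows the table and scores it. Because the region score is a maximum and the threshold is a rise of 1, one item can decide whether Trunk has progressed.

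The extrapolation rule treats a bounded, non-decreasing count as an unbounded straight line. It can therefore feed impossible values into the ANCOVA and inflate the variance of the outcome. This matters most in the analysis that drops data after PD medication, where trailing gaps will be frequent: the extension SAP, section 4.3.2, expects most patients to have started PD medication by year 1.

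A smaller gap is that Step 3 gives no rule for a change first seen at Week 52, the last Year 1 visit and also the first Year 2 dosing visit.

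**Working it through.** **(a) Item count.** Inputs: the Appendix IV table.

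| Region | Items |
|---|---|
| Right hand | 7 |
| Left hand | 7 |
| Right leg | 4 |
| Left leg | 4 |
| Trunk (3.3a, 3.9, 3.10, 3.12, 3.13) | 5 |
| Speech | 1 |
| Face | 2 |
| **Total** | **30** |

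The stated 30 is reproduced with 3.13 counted. Without it, Trunk has 4 items and the total is 29. Of the item numbers 3.1 to 3.18, the table omits 3.11, 3.14 and 3.18. The parenthesis names 3.11, 3.13 and 3.18, so the two lists differ in one entry only.

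**(b) Extrapolation.** Assumed example: confirmed counts 0, 1, 2, 4 at Weeks 0, 8, 16, 24, extrapolated to Week 52. The Week 24 count needs a usable Week 32 rating to confirm it. Week 32 is taken here as the first visit without a determinable count, because its own new changes have no confirming visit.

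- Last two points: slope (4 − 2)/8 = 0.25 per week; 4 + 0.25 × 28 = **11.0**.
- Least squares: mean week 12, mean count 1.75. Sxy = 21 + 3 + 1 + 27 = 52 and Sxx = 144 + 16 + 16 + 144 = 320, so the slope is 0.1625. Then 1.75 + 0.1625 × (52 − 12) = **8.25**.

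Both exceed 7. If a program instead carried the count of 4 to Week 32, the last-two-points slope would be 0 and the result 4. Least squares on 0, 1, 2, 4, 4 would give slope 88/640 = 0.1375 and 2.2 + 0.1375 × 36 = 7.15, still above 7. The SAP does not choose among these.

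With the last-two-points line, a subject whose last determined count is at Week 24, after a last step of +1, reaches c + 28/8 = c + 3.5. This exceeds 7 once c is 4 or more.

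**Size.** None of the inputs is in the SAP, so this is a simulation under stated assumptions: seven independent regions with a constant hazard, visits every 8 weeks to Week 48 plus Week 52, a last usable visit chosen at random among subjects with trailing gaps, trapezoid AUC, and no rating error.

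| Quantity | Result |
|---|---|
| Subjects above 7 at Week 52, hazards 0.3–1.0 per year, 10–50% trailing-missing | about 0.2% to 9% |
| Rise in AUC SD, same range | about 8% to 52% |
| AUC SD at hazard 0.6 and 50% missing | 0.88 complete, 1.21–1.23 extrapolated |

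At the highest hazard and missing fraction, a least-squares line takes the share above 7 to about 11%. At hazard 0.6 and 50% missing, capping at 7 removes only about a third of the SD inflation. The rest comes from extrapolation within the range 0 to 7.

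**(c) Weight of the Week 52 count.** Under Step 4's first definition, which averages visits before the current one, the weight is nil. Under the area definition, with an assumed 48-to-52-week interval, one extra region at Week 52 adds 0.5 × 4/52 = 0.04 (trapezoid) or 4/52 = 0.08 (step). Against an SD of 0.88 that is about 4% to 9% of one SD.

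**The case against.** **On posture**, the slip is probably clerical. The table is the working specification, it carries the SAS variable, and only it gives 30. That stands as the likeliest reading, but the document still says both things. A reader might go further and infer that 3.14 was certainly the intended exclusion. The SAP never names 3.14; it is inferred from a gap in the numbering, so the sponsor must confirm it.

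**On extrapolation**, trailing gaps should be much rarer in the analysis that keeps data after PD medication. The nearest figure in the SAP is the 10% dropout assumed at Week 52 (section 4), so the upper end of the missing range fits only the exclusion analysis. That stands. A reader might also build a starker case, such as counts of 1 at Week 8 and 3 at Week 16 followed by no usable data, giving 3 + (2/8) × 36 = 12. Step 3 does not allow it: with no visit after Week 16, the Week 16 changes are unconfirmed. From a confirmed 1 at Week 8 the line reaches 1 + (1/8) × 44 = 6.5, below 7. Impossible values need a longer confirmed trajectory, as in the example above.

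**On confirmation**, a reader might infer that Year 2 visits, after placebo subjects move to active drug, are used to confirm Week 52 changes and so break the placebo-controlled comparison. No text says so. Section 1 limits this SAP to Year 1, section 5.1.1 makes Week 52 the end-of-study visit for completers, and the Week 52 count carries little or no weight. What remains is an unstated last-visit rule.

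**On importance**, EP-RPS is neither primary nor listed as secondary in section 2 and receives no alpha in section 6. That also stands.

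**Conclusion.** The concern holds for two rules and as a clarification for a third. The 3.13 contradiction is certain from the text. Its effect on the number of progressed Trunk regions cannot be sized from the SAP. The possibility of more than 7 progressed regions follows directly from the Step 4 wording. How often it happens, and how much variance it adds, depend on assumed hazards, missing fractions and the fitting method, so the ranges indicate scale and are not estimates for this trial. The Week 52 confirmation gap has a small or nil effect on the Week 52 AUC. The consequences are confined to EP-RPS, its ANCOVA and its correlations; the primary analysis and its conclusion are untouched.

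**What to change.** - **Step 1:** remove 3.13 from the exclusion sentence so that it agrees with the 30-item table. The sponsor should confirm whether 3.14 was meant in its place.
- **Step 4:** cap imputed counts at 7, and state how the line is fitted. The cap removes impossible values but only part of the added variance, so it is a minimum repair.
- **Step 3:** state that a change first seen at Week 52 cannot be confirmed by visits after the first Year 2 infusion and is therefore not counted in the Year 1 score.

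The cost is a few lines in Appendix IV and the matching lines of the derivation program. No new data are needed.
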